Job bag number: REF-IBR6928, date of preparation October 2018

Study information

Title	Observational cohort study of patients with hormone receptor-positive metastatic breast cancer treated with palbociclib (Ibrance®) as part of the United Kingdom Ibrance® Patient Program (IPP); the Real Outcomes Ibrance® Study (ROIS)
Protocol number	X9001194
Protocol version identifier	1.0 Final
Date	12 November 2018
Active substance	Palbociclib - L01XE33
Medicinal product	Ibrance®
Research question and objectives	
What are the real-world treatment patterns, patients' characteristics, clinical outcomes and healthcare resource utilisation associated with palbociclib treatment in the 3 years following initiation in United Kingdom patients with hormone receptor-positive, human epidermal growth factor 2-negative metastatic breast cancer treated as part of the IPP?
 
Primary objectives:
 
• To describe patient demographic and clinical characteristics at initiation of palbociclib. 
Secondary objectives:
 
• To describe treatment pattern (as per licence/IPP requirement); including the proportion of patients with dose modification

	
and who switch treatment 1, 2 and 3 years after palbociclib initiation, and median time to dose modification and treatment discontinuation ('drug survival'). For patients who progress, to describe the 1st/2nd /3rd line of treatment after progression.
 
• To describe overall survival and progression-free survival, response (complete response, partial response), stable disease. This includes estimating the proportion of patients achieving those endpoints at 1, 2 and 3 years following palbociclib initiation; median survival, time to response and duration of response. In patients who respond to treatment, to describe partial response and complete response using "swimmer plots".• To describe the occurrence of neutropenia during the first year post-initiation observation period.• To describe the occurrence of gastro-intestinal toxicity, including diarrhoea, nausea and vomiting during the first year post-initiation observation period.• To describe progression of clinical indicators, including biochemical and radiological indicators at each time-point available during the first year following palbociclib treatment initiation (e.g. full blood counts, liver function tests, bone profile).• To describe breast cancer related healthcare resource utilisation (hospital admissions, outpatient visits, calls to Cancer National Services and contacts with the

2. LIST OF ABBREVIATIONS

Abbreviation	Definition
IPP	Ibrance® Patient Program
ROIS	Real Outcomes Ibrance® Study
HR+	Hormone Receptor Positive
BC	Breast Cancer
PFS	Progression-Free Survival
HER2(-)	Human Epidermal Growth Factor 2 (Negative)
MBC	Metastatic Breast Cancer
EU	European Union
NHS	National Health Service
NICE	National Institute for Health and Care Excellence
SMC	Scottish Medicines Consortium
UK	United Kingdom
CR	Complete Response
PR	Partial Response
OS	Overall Survival
AE	Adverse Event
CNS	Cancer National Service
AOS	Acute Oncology Service
IRB	Institutional Review Board
REC	Research Ethics Committee
CDK	Cyclin-Dependent Kinase
PALOMA	Palbociclib Ongoing Trials in the Management of Breast Cancer
US	United States
FDA	Food and Drug Administration
ENCePP	European Network of Centres for Pharmacoepidemiology and Pharmacovigilance

GDPR	General Data Protection Regulation
ISPE	International Society for Pharmacoepidemiology
eCRF	electronic Case Report Form
NCRI	National Cancer Research Institute
Y	Yes
N	No
NCI-DCI	National Cancer Institute - Deyo-Charlson Comorbidity Index
CI	Confidence Interval
A&E	Accident and Emergency
SAP	Statistical Analysis Plan
SD	Standard Deviation
SDV	Source Data Verification
EMA	European Medicines Agency
GDPR	General Data Protection Regulation
MHRA	Medicines and Healthcare products Regulation Regulatory Authority Agency
SRSD	Single Reference Safety Document
STROBE	Strengthening The Reporting of Observational studies in Epidemiology
ICMJE	International Committee of Medical Journal Editors

4. ABSTRACT

Title: Observational cohort study of patients with hormone receptor-positive metastatic breast cancer treated with palbociclib (Ibrance®) as part of the United Kingdom Ibrance® Patient Program (IPP); the Real Outcomes Ibrance® Study (ROIS)

Subtitle: the Real Outcomes Ibrance® Study (ROIS)

Hormone receptor positive (HR+) breast cancer (BC) represents the largest therapeutic subtype of the disease, accounting for 60 to 65% of all malignant neoplasms of the breast. Palbociclib (Ibrance®) is a small-molecule inhibitor of cyclin-dependent kinases 4 and 6 (CDK4/6) which in clinical trial settings has been shown to increase progression-free survival (PFS) for patients with HR+, human epidermal growth factor 2-negative (HER2-) metastatic breast cancer (MBC). Palbociclib first received a European Union (EU) marketing authorisation in September 2016, to be commercialised as Ibrance® by Pfizer. Palbociclib was recommended for use with an aromatase inhibitor in patients with HR+/HER2- locally advanced and MBC in the National Health Service (NHS) in England by the National Institute for Health and Care Excellence (NICE) in November 2017 and by the Scottish Medicines Consortium (SMC) in December 2017. In order to provide access to palbociclib in the United Kingdom (UK) during the NICE/SMC appraisal period, the Ibrance® Patient Program (IPP) was initiated and run by Pfizer between April 2017 until a positive NICE/SMC appraisal in November 2017 (for England and Wales) or December 2017 (for Scotland).

Pfizer are interested in the opportunity to collect data from patients who received palbociclib as part of the UK IPP, to better understand patients' characteristics in a routine care setting, treatment persistence and dose management, clinical outcomes, and healthcare resource utilisation. This study will provide real-world evidence on patients' clinical progression and experience of treatment with palbociclib in routine clinical settings in a UK context.

Research question:

What are the real-world treatment patterns, patients' characteristics, clinical outcomes and healthcare resource utilisation associated with palbociclib treatment in the 3 years following initiation in United Kingdom patients with HR+/HER2- MBC treated as part of the IPP?

Primary objectives:

- To describe patient demographic and clinical characteristics at initiation of palbociclib.

Secondary objectives

- To describe treatment pattern (as per licence/IPP requirement); including the proportion of patients with dose modification and who switch treatment 1, 2 and 3 years after palbociclib initiation, and median time to dose modification and treatment

discontinuation ('drug survival'). For patients who progress, to describe the 1st /2nd /3rd line of treatment after progression.

- To describe overall survival (OS) and progression-free survival (PFS), response (complete response [CR], partial response [PR]), stable disease. This includes estimating the proportion of patients achieving those endpoints at 1, 2 and 3 years following palbociclib initiation; median survival, time to response and duration of response. In patients who respond to treatment, to describe PR and CR using "swimmer plots".
- To describe the occurrence of neutropenia during the first year post-initiation observation period.
- To describe the occurrence of gastro-intestinal toxicity, including diarrhoea, nausea and vomiting during the first year post-initiation observation period.
- To describe progression of clinical indicators, including biochemical and radiological indicators at each time-point available during the first year following palbociclib treatment initiation (e.g. full blood counts, liver function tests, bone profile).
- To describe BC related healthcare resource utilisation (hospital admissions, outpatient visits, calls to Cancer National Services and contacts with the Acute Oncology Service) during the first year following palbociclib initiation.

This is an observational cohort study with retrospective and prospective data collection to obtain medical data covering the 3 year period following palbociclib initiation.

The study will be conducted in 8-9 NHS trusts across different regions within the UK (list of hospitals provided in Annex 1). In the hospitals selected for this study, approximately 250 patients received palbociclib as part of the IPP out of a total of 846 women who received palbociclib in the UK. Site selection was based upon a minimum of 15 patients being enrolled onto the IPP, except for one site selected) due to lead clinician's membership in the steering committee. Membership of the steering committee was based upon two criteria 1) membership of the National Cancer Research Institute (NCRI) MBC subcommittee and 2) had patients on the IPP. All members of the steering committee meet this criteria. The NCRI subcommittee is an independent committee from Pfizer, and Pfizer has no input into the committee as part of this study.

Patients will be eligible for this study if: (1) they received ≥ 1 dose of palbociclib as part of the IPP at one of the selected hospitals; (2) at sites where the data is collected by external researchers, patients provide consent for an external researcher to access their medical records (for living patients only). Patients were eligible for the IPP if palbociclib was used in combination with an aromatase inhibitor and patients had previously untreated HR+/HER2- locally advanced or MBC.

The following data will be collected from patients' medical records: demographic characteristics at time of initiation, medical history prior to palbociclib initiation, clinical

indicators of progression and response to treatment, occurrence of neutropenia and gastro-intestinal toxicity post-palbociclib initiation, and healthcare resource utilisation. PFS and OS will be estimated for patients from the date of initiation of palbociclib.

The analysis will be descriptive. Demographic characteristics and medical history will be described at the time of palbociclib initiation (baseline). Qualitative variables will be described by the absolute and relative (%) frequency of each class. Missing data will not be taken into account in the calculation of percentages (counts of missing observations will be included in a separate category). Quantitative variables will be described by their mean, standard deviation, median, 1st and 3rd quartiles, and extreme values (minimum and maximum), where applicable and the number of missing and non-missing values. The Kaplan-Meier method will be used to obtain estimates of median PFS, OS, CR, PR and time to discontinuation of palbociclib, with corresponding two-sided 95% confidence intervals.

Completion of retrospective data collection is planned for the 1st of February 2019. Completion of the prospective data collection is planned for the 1st of February 2021. An interim report on descriptive characteristics of patients already enrolled into the study (primary objective) will be produced in January 2019. Delivery of a 1-year report on the analysis of patients with 1-year follow-up post-initiation period (primary and secondary objectives) is planned for the 1st of July 2019. An additional 3-year report on the analysis of patients with up to 3-year follow-up post-initiation period (primary and secondary objectives) may be provided in July 2021.

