The following definitions will be implemented. PFS will be defined as the time from the date of palbociclib initiation to the date of first documented disease progression (i.e. mention of disease progression or mixed response in the medical records, e.g. due to evidence of a new site of disease, or increasing disease, after treatment initiation) or death. OS will be defined as the time from the date of palbociclib initiation until death from any cause. Time to achieving best overall response will be defined in patients who respond to treatment as the time from the date of palbociclib initiation until achievement of the best overall response: CR, or PR if CR is not achieved during follow-up. Duration of response will be defined as the time from the date CR or PR was first documented (whichever is recorded first) to the date of first documented disease progression or death from any cause (whichever occurs first).

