Definitions will be implemented as described in section 9.3 Variables. Patients who are known to be alive at the date of data collection (1-year for interim report and 3-year for full study report) will be censored at the date of data collection, and patients who are lost to follow-up will be censored on the date they were last known to be alive (e.g. date of last recorded hospital visit). Patients who are alive and free from disease progression at the date of data collection and those lost to follow-up will be censored on the date they were last known not to have disease progression (i.e. the date of last documented response assessment). Patients remaining in CR or PR at the end of the post-initiation observation period or lost to follow-up will be censored on the date CR or PR was last documented.

For the estimation of the proportion of patients alive, and free from disease progression, the denominator will be all patients known to be alive at the selected time-points (1 years, 2 years and 3 years). For the estimation of the proportion of patients achieving PR, CR and with stable disease at the selected time-points (1 years, 2 years and 3 years), the denominator will be all patients with at least one assessment of response (CR / PR / no response or stable disease / progressive disease) in the past year. Estimation of time to achieving best overall response and duration of response; and representation using swimmer plots will be performed in patients who respond (achieve CR or PR during follow-up) only.

Median PFS, OS, time to achieving best overall response, time to palbociclib dose modification and time to palbociclib discontinuation, and corresponding 95% CIs, will be estimated using Kaplan-Meier curves. Assessments of response (CR / PR / no response or stable disease / progressive disease) in patients responding to treatment (achieving CR or PR following initiation of palbociclib) will be represented using “swimmer plots”.

All percentages will be reported to the nearest whole number; therefore, in reporting study results in tables, figures and associated text, percentages may not add up to 100% due to rounding.

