9.9. Limitations of the research methods

- Comparisons of the results of this study with that of clinical trials and other real-world studies may be limited due to the presence of several potential sources of bias.
- Several sources of selection bias may be introduced in the study:

- At sites where data are collected by pH Associates, consent from living patients will be required; and consequently a low rate of consent amongst living patients may introduce an over-representation of deceased patients (for whom consent is not required) at those sites, and also compared to sites where consent is not required as all data are collected by the direct medical care team.
- Patients were treated as part of routine care and therefore patients enrolled in this study may have more diverse characteristics than in a clinical trial setting (for example with regard to menopausal status, ER and PR status, HER2 status), which may impact on the efficacy of palbociclib.
- Patients will be recruited from larger centres enrolled in the IPP, which may differ from smaller centres in terms of demographic and clinical characteristics, and therefore may not be representative of all patients treated with palbociclib in routine care as part of the IPP.
- Patients may be lost to follow-up due to the occurrence of AEs, lack of efficacy or other reasons, introducing attrition bias. However, the use of Kaplan-Meier curves will be used to obtain estimates of median PFS OS, CR, PR and this takes into account patient attrition.
- Radiological results will be collected from medical notes recorded by radiologists who were unblended to patient's treatment, introducing potential measurement bias.
- The interpretation of data collected retrospectively will be dependent on the completeness and quality of the medical records and the reliability of the abstraction of data from the medical records. However, SDV will be employed to identify and correct abstraction errors.
- This is a descriptive study and no analyses to control for confounding will be carried out; therefore, no definitive causal relationships between Ibrance® and study endpoints can be made.
- At sites where data are collected by pH Associates, a low consent rate may diminish sample size and the target of 250 patients enrolled into the study may not be achieved. If <200 patients are recruited into the study, an expansion of the study to other sites involved in the IPP will be considered.

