prescribed treatment in the 1st, 2nd, and 3rd line after palbociclib discontinuation was presented as a categoric variable as per section 8.1.2. Dose, duration of subsequent treatments and number of completed 28-day cycles per patient were presented as quantitative variables as per section 8.1.1. Number of completed 28-day cycles (categories: 1-6 cycles, 7-12 cycles, 13-18 cycles, 19-24 cycles, 25-27 cycles and No completed cycles) and the proportion of patients co-administered letrozole or fulvestrant were presented as categoric variables as per section 8.1.2. All other endpoints were evaluated as proposed.

8.2.3 Secondary Objective 2: To describe overall survival and progression-free survival, response (CR, PR), stable disease. This includes estimating the proportion of patients achieving those endpoints at 1 and 2 following palbociclib initiation: median survival, time to response and duration of response. In patients who respond to treatment, to describe PR and CR using “swimmer plots”.

Proposed: For the estimation of the proportion of patients alive, and free from disease progression, the denominator will be all patients known to be alive at the selected time-points (e.g., 1 years, 2 years, and 3 years). For the estimation of the proportion of patients achieving PR, CR and with stable disease at the selected time-points (1 years and 2 years), the denominator will be all patients with at least one assessment of response (CR / PR / no response or stable disease / progressive disease) in the past year.

[figure not shown]
Actual: Proportion of patients free from disease progression, are alive, achieved PR, CR or stable disease were analysed separately at the 2-year timepoint only. Length of follow-up, and time to best response and first response were presented as quantitative variables as per section 8.1.1. Best response to palbociclib, overall and by de novo and relapse status was treated as a categoric variable and analysed according to section 8.1.2.

8.2.4 Secondary Objective 3: To describe the occurrence of neutropenia during the first-year post-initiation observation period.

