Describing treatment patterns 1,2 and 3 years after palbociclib initiation	Full Analysis set	Secondary Objective 1	Overall and Treatment Line	Frequency tables and percentages for proportions of patients completing a 28-day cycle, co-administered letrozole and fulvestrant at palbociclib initiation. Summary statistics calculated (incl. Mean/Median/SD/IQR/Range) for number of completed 28-day cycles	Excluded
Proportion of patients free from disease progression	Full Analysis set	Secondary Objective 2	Overall and Treatment Line	Frequency tables and percentages	Excluded
Proportion of patients alive	Full Analysis set	Secondary Objective 2	Overall and Treatment Line	Frequency tables and percentages	Excluded
Proportion of patients achieving PR/CR/with stable disease	Full Analysis set	Secondary Objective 2	Overall and Treatment Line	Frequency tables and percentages	Excluded
Median PFS	Full Analysis set	Secondary Objective 2	Overall and Treatment Line	Kaplan-Meier analysis, median PFS measured as being time from the date of palbociclib initiation to the date of first document disease progression or death. 95% confidence intervals calculated for median.	Standard imputation for dates (section 7), otherwise exclude.
Median OS	Full Analysis set	Secondary Objective 2	Overall and Treatment Line	Kaplan-Meier analysis, median OS measured as being time from the date of palbociclib initiation to the date of death. 95% confidence intervals calculated for median.	Standard imputation for dates (section 7), otherwise exclude.
Median time to best overall response (CR or PR)	Full Analysis set	Secondary Objective 2	Overall and Treatment Line	Kaplan-Meier analysis, time to first best overall response (partial/complete response) measured as being time from the date of palbociclib initiation to the date of first response. 95% confidence intervals calculated for median.	Standard imputation for dates (section 7), otherwise exclude.
Swimmer plots	Full Analysis set	Secondary Objective 2	Overall and Treatment Line	Swimmer plots used to represent patient response (CR / PR/ stable disease / progressive disease) to treatment for patients responding to treatment (CR or PR).	
Duration of response (PR/CR)	Patients enrolled achieving PR/CR	Secondary objective 2	Overall and Treatment Line	Kaplan-Meier analysis, median duration of response measured as being time from the	Standard imputation for dates (section 7),

PFIZER CONFIDENTIAL

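### Time to response is given conflicting populations and methods, and one written option (Kaplan-Meier in the Full Analysis Set, no rule for progression or death before response) would be biased

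*Protocol*

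**What the plan says.** Two sets of statements do not agree.

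**Kaplan-Meier, population wide or unstated**
- Protocol abstract: "The Kaplan-Meier method will be used to obtain estimates of median PFS, OS, CR, PR and time to discontinuation of palbociclib". It gives no population, event or censoring rule for CR or PR.
- Protocol 9.9, on attrition bias: "Kaplan-Meier curves will be used to obtain estimates of median PFS OS, CR, PR and this takes into account patient attrition".
- SAP table 8.2.9, row on median time to best overall response: "Kaplan-Meier analysis, time to first best overall response (partial/complete response) measured as being time from the date of palbociclib initiation". The analysis set is the Full Analysis Set, and a 95% CI for the median is planned. The duration-of-response row of the same table is limited to "Patients enrolled achieving PR/CR" during follow-up.

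**Responders only, or a descriptive summary**
- Protocol 9.3, repeated in SAP section 6: "Time to achieving best overall response will be defined in patients who respond to treatment".
- Protocol 9.7: "Estimation of time to achieving best overall response and duration of response; and representation using swimmer plots will be performed in patients who respond", meaning those who reach CR or PR. The same section names Kaplan-Meier for the median.
- SAP 8.2.3, paragraph marked Actual: "Length of follow-up, and time to best response and first response were presented as quantitative variables as per section 8.1.1".

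The only response-related censoring rule (Protocol 9.7, SAP 8.2) covers patients already in CR or PR. Neither document says how to treat a patient who progresses or dies without having responded.

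**The concern.** Kaplan-Meier knows only events and censoring. In the Full Analysis Set, some patients progress or die before any response. If an analyst follows the table row and censors them there, the estimate assumes they would have gone on to respond at the same rate as those still at risk. One minus Kaplan-Meier then exceeds the share of patients who actually respond, and the curve can cross 50% when fewer than half ever do. A reader could take that curve and its median as the chance and timing of response to palbociclib in UK practice.

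The attrition remark in Protocol 9.9 encourages the whole-cohort reading. Among responders every patient has the event and nobody is censored before it, so for response there would be no attrition to account for.

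**Working it through.** **No figure to reproduce.** The documents state no response rate and no expected median time to response. What follows sizes the biased option only.

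**Inputs.** The competing event is progression or death, with median 24.8 or 20.2 months (the PALOMA-2 and PALOMA-1 palbociclib arms, Protocol section 7). The horizon is 24 months (SAP 8.1 uses 2-year data). N is about 200 (SAP 2.1). The true cumulative response of 30% or 40% is an assumption.

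**Model A, constant hazards.** Let p = ln2/median be the competing hazard and r the response hazard.
- True cumulative incidence at T: r/(r+p) × [1 − exp(−(r+p)T)]
- One minus Kaplan-Meier at T: 1 − exp(−rT)
- Kaplan-Meier median: ln2/r

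Example with median 24.8 and 40% true response at 24 months: p = ln2/24.8 = 0.02795, and solving gives r = 0.03121. Check: 0.03121/0.05916 × [1 − exp(−1.420)] = 0.5276 × 0.758 = 0.400. One minus Kaplan-Meier = 1 − exp(−0.749) = 0.527. Median = ln2/0.03121 = 22.2 months, although 60% have not responded.

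**Model A, early version.** The same formulas with T = 12 and no responses afterwards.

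**Model B, scan-based early response.** Responders respond at months 3, 6, 9 and 12 in shares of 40/30/20/10%, and non-responders are censored at exponential progression. Example with 30% response and median 24.8: the fractions at risk just before each scan are 0.9437, 0.7719, 0.6343 and 0.5306, with events 0.12, 0.09, 0.06 and 0.03. The survival product is 0.8728 × 0.8834 × 0.9054 × 0.9435 = 0.659, so one minus Kaplan-Meier is 0.341. A simulation of 200,000 patients gave the same value.

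| True response | Competing median (months) | Model A, T=24 | Model A, T=12 | Model B |
|---|---|---|---|---|
| 30% | 24.8 | 40.0% | 34.9% | 34.1% |
| 30% | 20.2 | 42.4% | 36.1% | 35.2% |
| 40% | 24.8 | 52.7% | 46.3% | 44.8% |
| 40% | 20.2 | 55.6% | 47.7% | 46.0% |

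The excess runs from 34.1 − 30 = 4.1 points to 55.6 − 40 = 15.6 points. For scale, the standard error of a proportion at N = 200 is √(0.3×0.7/200) = 3.2 points, or √(0.4×0.6/200) = 3.5 points.

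**Spurious median.** At 40% response, Model A with T=24 gives a median of 22.2 or 20.5 months. At 30% it gives none. When responses end by month 12, none appears at 30% or 40%. With the 24.8-month competing median, Model B reaches 50% only at 45% true response (barely) or above.

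**Responders-only reading.** Everyone in the set has the event and no censoring precedes it. Kaplan-Meier is then the empirical distribution and its median is the sample median, so no competing-risk bias arises. The result is conditional on having responded.

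**The case against.** The strongest reply is that the biased analysis is not what the documents plan. Much of that stands.

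- The endpoint definition in both documents excludes non-responders, and Protocol 9.7 confines estimation to responders.
- The Full Analysis Set label is loose evidence. It is the only analysis set the SAP defines, and the swimmer-plot row carries it while its method column restricts the plot to responders.
- SAP 8.2 says that some proposed analyses were not conducted and were kept as a record, and the Actual paragraph in 8.2.3 describes summary statistics.
- SAP 8.1.3 offers Kaplan-Meier only as an option, and only for survival-related endpoints.
- The bias needs censoring at progression or death, which no text prescribes. Non-responders could be kept at risk to the end of observation. With complete follow-up, one minus Kaplan-Meier would then equal the cumulative incidence.

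A reader might therefore infer too much: that the plan treats progression and death as censoring in the whole cohort, so that its reported probability of response is overstated. The documents do not support this. Only one table row names the whole cohort, the abstract and Protocol 9.9 name no population, and CR, PR and stable disease are reported as simple proportions with their own denominator.

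The reply does not remove the contradiction. SAP section 6, which says it reflects the analyses conducted, still lists a median with 95% CI for time to best overall response. The section 8.1.1 summary that 8.2.3 refers to gives a median with IQR, not a CI for the median. The row in table 8.2.9 was left unchanged. It also mixes two endpoints, naming best overall response but measuring to the date of first response.

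**Conclusion.** The concern holds as an internal contradiction on population (Full Analysis Set or responders) and method (Kaplan-Meier median with CI or descriptive summary). It is accompanied by an undefined median of CR and PR and by a missing rule for progression or death before response. One of the written options is biased if non-responders are censored at those events. The illustrative size is 4 to 16 points, resting on an assumed 30-40% response, a competing median of 20 to 25 months borrowed from the trials cited in the Protocol, and the assumed timing of responses. The upper end needs responses spread over two years; early responses give about 4 to 8 points. The responders-only analysis is free of this bias but says nothing about how often patients respond. This is a secondary endpoint in a descriptive study, so the weight is moderate, and correction is worthwhile because it costs almost nothing.

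**What to change.** 1. Delete CR and PR from the Kaplan-Meier sentences in the Protocol abstract and Protocol 9.9.
2. In SAP table 8.2.9, change the time-to-best-response row to a plain median and IQR among responders, labelled as conditional on response. Use one end date, matching the definition in Protocol 9.3 and SAP section 6, and bring the median-with-CI entry in section 6 into line. If time to first response is also reported, give it its own row.
3. If a whole-cohort result is wanted, replace Kaplan-Meier by the Aalen-Johansen cumulative incidence of first CR or PR, with progression and death as competing events, at 12 and 24 months with 95% CI.

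Steps 1 and 2 are wording only. Step 3 needs a little code and no new data, because dates of response, progression and death are already collected.
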